7.2.3 Immediate Reporting of Adverse Events to the Sponsor and to Merck

7.2.3.1 Serious Adverse Events

A serious adverse event is any adverse event occurring at any dose or during any use of Merck's product that:

- Results in death;
- Is life threatening;
- Results in persistent or significant disability/incapacity;
- Results in or prolongs an existing inpatient hospitalization;
- Is a congenital anomaly/birth defect;
- Is another important medical event.
- **Note:** In addition to the above criteria, adverse events meeting either of the below criteria, although not serious per ICH definition, are reportable to the Merck in the same timeframe as SAEs to meet certain local requirements. Therefore, these events are considered serious by Merck for collection purposes.
 - Is a new cancer (that is not a condition of the study);
 - Is associated with an overdose.

Refer to Table 6 for additional details regarding each of the above criteria.

For the time period beginning when the consent form is signed until treatment allocation/randomization, any serious adverse event, or follow up to a serious adverse event, including death due to any cause that occurs to any subject must be reported within 24 hours to the Sponsor and within 2 working days to Merck Global Safety if it causes the subject to be excluded from the trial, or is the result of a protocol-specified intervention, including but not limited to washout or discontinuation of usual therapy, diet, placebo treatment or a procedure.

For the time period beginning at treatment allocation/randomization through 90 days following cessation of treatment, or 30 days following cessation of treatment if the subject initiates new anticancer therapy, whichever is earlier, any serious adverse event, or follow up to a serious adverse event, including death due to any cause whether or not related to the Merck product, must be reported within 24 hours to the Sponsor and within 2 working days to Merck Global Safety.

Additionally, any serious adverse event, considered by an investigator who is a qualified physician to be related to Merck product that is brought to the attention of the investigator at any time following consent through the end of the specified safety follow-up period specified

in the paragraph above, or at any time outside of the time period specified in the previous paragraph also must be reported immediately to the Sponsor and to Merck Global Safety.

All subjects with serious adverse events must be followed up for outcome.

SAE reports and any other relevant safety information are to be forwarded to the Merck Global Safety [contact]

A copy of all 15 Day Reports and Annual Progress Reports is submitted as required by FDA, European Union (EU), Pharmaceutical and Medical Devices agency (PMDA) or other local regulators. Investigators will cross reference this submission according to local regulations to the Merck Investigational Compound Number (IND, CSA, etc.) at the time of submission. Additionally investigators will submit a copy of these reports to Merck & Co., Inc. (Attn: Worldwide Product Safety; [contact]) at the time of submission to FDA.

7.2.3.2 Events of Clinical Interest

Selected non-serious and serious adverse events are also known as Events of Clinical Interest (ECI) and must be reported within 24 hours to the Sponsor and within 2 working days to Merck Global Safety. (Attn: Worldwide Product Safety; [contact]).

For the time period beginning when the consent form is signed until treatment allocation/randomization, any ECI, or follow up to an ECI, that occurs to any subject must be reported within 24 hours to the Sponsor and within 2 working days to Merck Global Safety if it causes the subject to be excluded from the trial, or is the result of a protocol-specified intervention, including but not limited to washout or discontinuation of usual therapy, diet, placebo treatment or a procedure.

For the time period beginning at treatment allocation/randomization through 90 days following cessation of treatment, or 30 days following cessation of treatment if the subject initiates new anticancer therapy, whichever is earlier, any ECI, or follow up to an ECI, whether or not related to Merck product, must be reported within 24 hours to the Sponsor and within 24 hours to Merck Global Safety.

Events of clinical interest for this trial include:

1. an overdose of Merck product, as defined in Section 7.2.1 - Definition of an Overdose for This Protocol and Reporting of Overdose to the Sponsor, that is not associated with clinical symptoms or abnormal laboratory results.
2. an elevated AST or ALT lab value that is greater than or equal to 3X the upper limit of normal and an elevated total bilirubin lab value that is greater than or equal to 2X the upper limit of normal and, at the same time, an alkaline phosphatase lab value that is less than 2X the upper limit of normal, as determined by way of protocol-specified laboratory testing or unscheduled laboratory testing.*

***Note:** These criteria are based upon available regulatory guidance documents. The purpose of the criteria is to specify a threshold of abnormal hepatic tests that may require an additional evaluation for an underlying etiology.

7.2.4 Evaluating Adverse Events

An investigator who is a qualified physician will evaluate all adverse events according to the NCI Common Terminology for Adverse Events (CTCAE), version 4.0. Any adverse event which changes CTCAE grade over the course of a given episode will have each change of grade recorded on the adverse event case report forms/worksheets.

All adverse events regardless of CTCAE grade must also be evaluated for seriousness.

Table 6 Evaluating Adverse Events

An investigator who is a qualified physician, will evaluate all adverse events as to:

V4.0 CTCAE Grading	Grade 1	Mild; asymptomatic or mild symptoms; clinical or diagnostic observations only; intervention not indicated.
	Grade 2	Moderate; minimal, local or noninvasive intervention indicated; limiting age-appropriate instrumental ADL.
	Grade 3	Severe or medically significant but not immediately life-threatening; hospitalization or prolongation of hospitalization indicated; disabling; limiting self-care ADL.
	Grade 4	Life threatening consequences; urgent intervention indicated.
	Grade 5	Death related to AE
Seriousness	A serious adverse event is any adverse event occurring at any dose or during any use of Merck product that:	
	† Results in death ; or	
	† Is life threatening ; or places the subject, in the view of the investigator, at immediate risk of death from the event as it occurred (Note: This does not include an adverse event that, had it occurred in a more severe form, might have caused death.); or	
	† Results in a persistent or significant disability/incapacity (substantial disruption of one's ability to conduct normal life functions); or	
	† Results in or prolongs an existing inpatient hospitalization (hospitalization is defined as an inpatient admission, regardless of length of stay, even if the hospitalization is a precautionary measure for continued observation. (Note: Hospitalization for an elective procedure to treat a pre-existing condition that has not worsened is not a serious adverse event. A pre-existing condition is a clinical condition that is diagnosed prior to the use of a Merck product and is documented in the patient's medical history.); or	
	† Is a congenital anomaly/birth defect (in offspring of subject taking the product regardless of time to diagnosis); or	
	Is a new cancer (that is not a condition of the study) (although not serious per ICH definition, is reportable to the Sponsor within 24 hours and to Merck within 2 working days to meet certain local requirements); or	
	Is an overdose (whether accidental or intentional). Any adverse event associated with an overdose is considered a serious adverse event for collection purposes. An overdose that is not associated with an adverse event is considered a non-serious event of clinical interest and must be reported within 24 hours to the Sponsor and to Merck within 2 working days..	
	Other important medical events that may not result in death, not be life threatening, or not require hospitalization may be considered a serious adverse event when, based upon appropriate medical judgment, the event may jeopardize the subject and may require medical or surgical intervention to prevent one of the outcomes	

	listed previously (designated above by a †).
Duration	Record the start and stop dates of the adverse event. If less than 1 day, indicate the appropriate length of time and units
Action taken	Did the adverse event cause Merck product to be discontinued?
Relationship to Merck Product	
Did Merck product cause the adverse event? The determination of the likelihood that Merck product caused the adverse event will be provided by an investigator who is a qualified physician. The investigator's signed/dated initials on the source document or worksheet that supports the causality noted on the AE form, ensures that a medically qualified assessment of causality was done. This initialed document must be retained for the required regulatory time frame. The criteria below are intended as reference guidelines to assist the investigator in assessing the likelihood of a relationship between the test drug and the adverse event based upon the available information.
 
The following components are to be used to assess the relationship between Merck product and the AE; the greater the correlation with the components and their respective elements (in number and/or intensity), the more likely Merck product caused the adverse event (AE):
 
Exposure Is there evidence that the subject was actually exposed to Merck product such as: reliable history, acceptable compliance assessment (pill count, diary, etc.), expected pharmacologic effect, or measurement of drug/metabolite in bodily specimen?
 
Time Course Did the AE follow in a reasonable temporal sequence from administration of Merck product? Is the time of onset of the AE compatible with a drug-induced effect (applies to trials with investigational medicinal product)?
 
Likely Cause Is the AE not reasonably explained by another etiology such as underlying disease, other drug(s)/vaccine(s), or other host or environmental factors

Relationship to Merck Product (continued)		The following components are to be used to assess the relationship between the test drug and the AE: (continued)	
	Dechallenge	
Was Merck product discontinued or dose/exposure/frequency reduced?
 
If yes, did the AE resolve or improve?
 
If yes, this is a positive dechallenge. If no, this is a negative dechallenge.
 
(Note: This criterion is not applicable if: (1) the AE resulted in death or permanent disability; (2) the AE resolved/improved despite continuation of the Sponsor's product; or (3) the trial is a single-dose drug trial); or (4) Sponsor's product(s) is/are only used one time.)
	
	Rechallenge	
Was the subject re-exposed to Merck product in this study?
 
If yes, did the AE recur or worsen?
 
If yes, this is a positive rechallenge. If no, this is a negative rechallenge.
 
(Note: This criterion is not applicable if: (1) the initial AE resulted in death or permanent disability, or (2) the trial is a single-dose drug trial); or (3) Sponsor's product(s) is/are used only one time).
 
NOTE: IF A RECHALLENGE IS PLANNED FOR AN ADVERSE EVENT WHICH WAS SERIOUS AND WHICH MAY HAVE BEEN CAUSED BY MERCK PRODUCT, OR IF REEXPOSURE TO MERCK PRODUCT POSES ADDITIONAL POTENTIAL SIGNIFICANT RISK TO THE SUBJECT, THEN THE RECHALLENGE MUST BE APPROVED IN ADVANCE BY THE SPONSOR AS PER DOSE MODIFICATION GUIDELINES IN THE PROTOCOL.
	
	Consistency with Trial Treatment Profile	Is the clinical/pathological presentation of the AE consistent with previous knowledge regarding Merck product or drug class pharmacology or toxicology?	
The assessment of relationship will be reported on the case report forms /worksheets by an investigator who is a qualified physician according to his/her best clinical judgment, including consideration of the above elements.			
Record one of the following		Use the following scale of criteria as guidance (not all criteria must be present to be indicative of Merck product relationship).	
Yes, there is a reasonable possibility of Merck product relationship.		There is evidence of exposure to Merck product. The temporal sequence of the AE onset relative to the administration of Merck product is reasonable. The AE is more likely explained by Merck product than by another cause.	
No, there is not a reasonable possibility of Merck product relationship		Subject did not receive the Merck product OR temporal sequence of the AE onset relative to administration of Merck product is not reasonable OR the AE is more likely explained by another cause than the Merck product. (Also entered for a subject with overdose without an associated AE.)	

7.2.5 Sponsor Responsibility for Reporting Adverse Events

All Adverse Events will be reported to regulatory authorities, IRB/IECs and investigators in accordance with all applicable global laws and regulations.

8.0 STATISTICAL ANALYSIS PLAN

8.1 Statistical Analysis Plan Summary

The target sample size of this prospective, single-arm, phase 2 study is 26 patients. The estimated time for patient accrual is 2 years. It takes a minimum of additional 3 years to complete the follow up of the last accrued patient. The total study period is planned to be 5 years.

The primary objective of the study is to improve the 1-year RFS rate for locally advanced ESCC patients who have received preoperative cisplatin-based CRT followed by surgery, and exhibit high risk of tumor recurrence. The secondary objectives of the study included the median recurrence-free survival, overall survival and overall survival rate, and safety and toxicity. According to the subgroup analysis of our previous study [12], the median RFS for locally advanced ESCC patients who have received preoperative cisplatin-based CRT followed by surgery, and exhibit high risk of tumor recurrence (defined as closed or involved margin [$\leq 1\text{mm}$] or ENI or ypN2-3) is 6.7 months, equivalent to a 1-year RFS rate of 32.3%.

8.2 Statistical Analysis Plan

8.2.1 Sample Size Determination

According to the subgroup analysis of our previous study [12], the median RFS for locally advanced ESCC patients who have received preoperative cisplatin-based CRT followed by surgery, and exhibit high risk of tumor recurrence (defined as closed or involved margin [$\leq 1\text{mm}$] or ENI or ypN2-3) is 6.7 months, equivalent to a 1-year RFS rate of 32.3%. It would need a sample size of 24 patients to detect a difference of the 1-year RFS rate from 32% to 60% by calculated using an exact binomial test with a power of 80% and a 5% significance level. Having taken an additional 10% of early drop-out rate into consideration, the total enrolled patient number will be 26 for this study. We estimate an enrollment rate of 12 patients per year at my center. Therefore, total study period will be 5 years, including 2 years of patient enrollment and 3 years of patient follow-up.

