Duration of Participation	
Subjects need to sign the informed consent form to be enrolled into this trial.After a screening phase up to 28 days, each subject will receive adjuvant weekly cisplatin -CRT (cisplatin, 30mg/m²/week x 2; radiotherapy, 180-200 cGy/fraction x 10-13) followed by pembrolizumab (200mg/3 weeks x 18) (approx. a total of 56 weeks).Treatment will continue until the completion of the planned cisplatin-CRT plus 18 cycles of pembrolizumab, or until recurrent disease, unacceptable adverse events, intercurrent illness that prevents further administration of treatment, investigator's decision to withdraw the subject, subject withdrawal of consent, pregnancy of the subject, noncompliance with trial treatment, or administrative reasons requiring cessation of treatment.To detect the tumor recurrence, all patients will be evaluated by pertinent evaluation and imaging studies every 4 cycles of pembrolizumab during treatment phase, then every 3 months for post-treatment year-1 to year-2, and every 6 months for post-treatment year-3 and year-4.Subjects who discontinue for reasons other than recurrent disease will have post-treatment follow-up visits for monitoring disease status as if they were still on treatment until recurrent disease, initiating a non-study cancer treatment, withdrawing consent from study participation, or becoming lost to follow-up.All subjects will be followed (e.g., by telephone or visit) for overall survival until death, withdrawal of consent from study participation, or the end of the study, whichever comes first. After the end of study treatment, each subject will be followed for 30 days for adverse event monitoring. Serious adverse events will be

	collected for 90 days after the end of treatment or for 30 days after the end of treatment if the subject initiates new anticancer therapy, whichever is earlier.
Estimated average length of treatment per patient	56 weeks

[figure not shown]

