2.0 TRIAL DESIGN

2.1 Trial Design

It is a single-arm phase II trial. The target population is patients with histologically diagnosed locally advanced ESCC patients (clinically staged at least T3 and/or any N and M0 by endoscopic ultrasonography [EUS] and fludeoxyglucose-positron emission tomography [FDG-PET]) who have received preoperative cisplatin-based chemoradiotherapy (CRT) followed by surgery, and exhibit high risk of tumor recurrence. Eligible patients will receive adjuvant cisplatin-based CRT followed by pembrolizumab for 18 cycles.

The study hypothesizes that adjuvant cisplatin-based CRT followed by pembrolizumab will improve the 1-year relapse-free survival rate for these high-risk ESCC patients from 32% to 60%. With the two-sided type 1 error probability of 0.05 and type 2 error probability of 0.2, the study needs to enroll a total of 26 patients, taking another 10% of dropout rate. The duration of patient accrual is expected as 24 months. To detect the mature overall survival data, additional follow-up period of 36 months is needed.

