8.2.2 Definition of Variables

8.2.2.1 Recurrence-free survival is the time from enrollment to disease recurrence or the last follow-up (censored). Recurrence is defined by suspicious lesion noted by tumor imaging according to RECIST 1.1. Tissue proof for suspicious lesion is recommended if it is feasible.

8.2.2.2 Overall survival is the time from enrollment to death of any cause or the last follow-up (censored).

8.2.2.3 Evaluation of Toxicity: The incidence and severity of toxicity will be summarized according to the NCI Common Toxicity Criteria Version 4.0.

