8.2.3 General Statistical Consideration

8.2.3.1 All statistical analyses will be performed for intent-to-treatment population.

8.2.3.2 The survival estimates will be derived from Kaplan and Meier curves.

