10.6 Data Management

All available data will be displayed. Listings of patients with premature termination will be provided with the dates and reasons for termination. Missing data will not be replaced by any estimated or imputed values.

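### At the plan's own 10% loss, power is about 70–80% depending on an unnamed primary analysis, and the exact test used for sizing has no rule for patients censored before 12 months

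*Combined protocol and SAP*

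**What the plan says.** Section 2.1 gives the error rates for detecting an improvement from 32% to 60%: "With the two-sided type 1 error probability of 0.05 and type 2 error probability of 0.2". Section 8.2.1 gives 24 patients, "calculated using an exact binomial test with a power of 80% and a 5% significance level", without repeating the sidedness. It then says: "Having taken an additional 10% of early drop-out rate into consideration, the total enrolled patient number will be 26 for this study". Section 5.9 rules out replacing patients.

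The analysis text reads differently from the sizing text:

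- Section 8.2.2.1: "Recurrence-free survival is the time from enrollment to disease recurrence or the last follow-up (censored").
- Section 8.2.3: "All statistical analyses will be performed for intent-to-treatment population", and "The survival estimates will be derived from Kaplan and Meier curves".
- Section 10.6: "Missing data will not be replaced by any estimated or imputed values".

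On follow-up, section 1.0 says that patients who stop treatment without recurrence have "post-treatment follow-up visits for monitoring disease status as if they were still on treatment". Section 5.8 says much the same. No section names the test or interval that is compared with 32%.

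**The concern.** Two things are at issue. The dropout allowance is meant to protect the stated 80% power, yet 26 × 0.9 = 23.4, which is below the 24 required. The power under the planned loss therefore has to be checked.

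The test used for sizing also cannot be applied as it stands to the data that the analysis text describes. An exact binomial test counts successes among patients whose 12-month status is known. A patient censored at month 5 is neither a success nor a failure, remains in the analysis set, and may not be given an imputed status. Kaplan-Meier handles such a patient, but section 8.2.3 mentions it only for estimates. In an open-label single-arm trial judged against a historical rate, an unnamed decision rule leaves a borderline result open to whichever method is chosen once the data are in.

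**Working it through.** **Inputs.** Null rate 0.32, alternative 0.60, exact binomial test, 24 patients, 26 enrolled, 10% dropout (8.2.1); two-sided 0.05 (2.1); no replacement (5.9).

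**Step 1: the plan's own figure.** With X ~ Binomial(n, p), find the smallest r with P(X ≥ r | 0.32) ≤ 0.025; power is P(X ≥ r | 0.60).

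- n = 24: r = 13, upper tail 0.0202, power 78.7%. The minimum-likelihood two-sided test has the same boundary. This agrees with 80% to rounding.
- n = 26, all 12-month statuses known: r = 14, upper tail 0.0172, power 80.1%.

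**Step 2: loss at the start.** Let the number remaining be M ~ Binomial(26, 0.9), and average the power over M with the boundary recomputed for each M. With no later censoring, the Kaplan-Meier estimate is the simple proportion among those remaining, so its limits are exact functions of the count.

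**Step 3: loss spread uniformly over year 1.** This was simulated with at least 100,000 runs, assuming exponential event times and loss unrelated to outcome. The exact test uses patients with known 12-month status. It loses power here because a patient who relapses before being lost is a known failure, while one lost relapse-free is dropped.

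Power at a true 60%, 26 enrolled:

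| Analysis | 10% loss, start | 10% loss, spread | 5% loss, start | 5% loss, spread | No loss |
|---|---|---|---|---|---|
| Exact, equal-tail | 74.4% | 70.4% | 76.2% | 74.4% | 80.1% |
| Exact, minimum-likelihood | 77.3% | 73.0% | 77.4% | 75.2% | 80.1% |
| Kaplan-Meier, log-log limit | 74.4% | 75.5% | 76.2% | 77.4% | 80.1% |
| Kaplan-Meier, plain limit | 77.1% | 79.7% | 80.3% | 80.8% | 80.1% |

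With no loss, all four share the 14-of-26 boundary.

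**Step 4: where the gap comes from.** 24 / 0.9 = 26.7, which rounds up to 27. With 27 enrolled and 10% lost at the start, the exact test gives 75.5% (equal-tail) or 78.0% (minimum-likelihood), against 74.4% and 77.3% with 26. Rounding down thus costs about 1 point. The rest is the loss itself and the saw-tooth of the exact test. At n = 25 both versions need 14 and give 73.2%. At n = 23 equal-tail needs 13 (71.3%), while minimum-likelihood needs 12 (83.6%).

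**Step 5: can the choice reverse a verdict?** Plain limit: s − 1.96·√(s(1 − s)/n). Log-log limit: exp{−exp[log(−log s) + 1.96·√((1 − s)/(n·s))/|log s|]}.

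- One lost at the start, 13 of 25 relapse-free (s = 0.52). The plain limit is 0.52 − 1.96 × 0.0999 = 32.4%, a success. The log-log limit is 31.2% and the minimum-likelihood p is 0.051, both failures. The upper tail is 0.0299, so equal-tail fails too.
- Three lost, 12 of 23 (s = 0.522). The minimum-likelihood p is 0.045, a success. Equal-tail fails (upper tail 0.0354), as do the log-log limit (30.5%) and the plain limit (31.8%).

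At a true 60% and 10% loss, pairs of these four rules disagree in 0 to 5.4% of trials (loss at the start) or 2.7 to 9.3% (spread).

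**Step 6: error at a true 32%.** Averaged over the loss, the upper-tail error is at most about 1.7% for log-log and about 2.3% for plain. At particular numbers remaining plain can exceed 2.5%: with 25 it accepts 13, whose upper tail is 2.99%.

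**The case against.** The strongest reply is that the sizing is sound. 24 patients give 80% to rounding. Adding 10% to 24 gives 26.4, so 26, and losing exactly two patients leaves the 24 required. All of that is correct and explains the 26. It does not restore 80% under a 10% loss, because 10% of 26 is 2.6 and the number lost varies.

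A second reply is that Kaplan-Meier on all enrolled patients is the natural reading of 8.2.3, and with a plain interval and spread loss it gives 79.7%. This stands: on that reading the shortfall is roughly 0 to 6 points. But no section ties that estimate to a comparison with 32%, or names the interval scale.

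A third is that real loss may be below 10%, since disease follow-up continues after treatment stops (1.0, 5.8). This also stands. At 5% the gap is smaller, and with no loss it is gone.

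A fourth is that 8.2.1 does not repeat the sidedness. A one-sided 0.05 exact test would average 81.6% at 10% loss. Section 2.1, however, says two-sided.

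**Conclusion.** The point holds, at moderate weight. At the plan's own 10% loss and two-sided 0.05, power is about 70–77% for the exact test and 74–80% for Kaplan-Meier, and the plan does not say which applies. The missing decision rule matters more than the few points of power, because one to three losses are enough for the choice of method to settle a borderline result.

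Stronger readings that a reader might infer are not supported:

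- That the sample size is miscalculated, or that enrolling 26 rather than 27 causes the shortfall. The 24 reproduces, and the 27th patient is worth about 1 point to the exact test.
- That intent-to-treat analysis means counting lost patients as failures. This would give a success probability of 0.6 × 0.9 = 0.54 and power of 58.6% with 14 of 26 needed. No section says so, and 10.6 bars filling in missing values.

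The figures assume that loss is unrelated to outcome and, for spread loss, exponential event times. They treat every patient as either relapse-free at 12 months or having an RFS event. Section 8.2.2.1 lists only recurrence, so how a death without recurrence counts must be stated for them to apply.

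**What to change.** In 8.2.3, before outcome data are reviewed, name one primary analysis. A suitable choice is the Kaplan-Meier 12-month RFS rate in all enrolled patients, with success if the lower limit of the two-sided 95% interval exceeds 32% on one named scale. Log-log is the safer scale in view of step 6.

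In 2.1 and 8.2.1, restate the power of that analysis at 10% loss: about 74–76% for log-log, or 77–80% for plain. Say that 78.7% (24 patients) and 80.1% (26 patients) apply to complete data only.

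If the exact test is kept instead, state its two-sided version, how patients censored before 12 months count, and power of about 70–77%. A sensitivity analysis that counts lost patients as failures would need a stated exception to 10.6.

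Keep the sample size at 26. The cost is a few sentences and a slightly lower stated power, with no extra patients or data.
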